### 6.3 Data Collection

The following data will be collected:

#### Pre-operative/Baseline

- DOB
- Name
- Gender
- Race
- Ethnicity
- Height, weight, BMI
- ASA
- MRN

- Preop NRS
- Preop Sensory tests
- Preop Brief Pain Inventory

**Surgical procedure (Intra-operative)**

- Surgeon and Anesthesiologist
- Surgery start and end
- Length of Surgery
- Anesthesia start and end
- Induction start and end
- Type of Shoulder surgery
- Laterality
- Intraoperative fentanyl and dilaudid use

**Post-Operative Day 0 (PACU)**

- Vital Signs (systolic bp, diastolic bp, pulse)
- Ambulation (steady gait/no dizziness, requires assistance, unable to ambulate/dizziness)
- Nausea and Vomiting
- Pain (NRS)
- Surgical bleeding
- Length of PACU stay (OR to PACU transfer time, PACU discharge time)

**Post-Operative Day 1 (POD 1)**

- NRS
- Brief pain inventory
- Medication Usage
- Block Resolution
- Side Effects
- Satisfaction

**Post-Operative Day 2 (POD 2)**

- NRS
- Brief pain inventory
- Medication Usage
- Block Resolution
- Side Effects
- Satisfaction

**Post-Operative Day 3 (POD 3)**

- NRS
- Brief pain inventory
- Medication Usage
- Block Resolution
- Side Effects
- Satisfaction and Blinding

**Post-Operative Day 4 (POD 4)**

- NRS
- Brief pain inventory
- Medication Usage
- Block Resolution
- Side Effects
- Satisfaction

**Post-Operative Day 7 (POD 7)**

- NRS
- Brief pain inventory
- Medication Usage
- Side Effects
- Satisfaction

**Post-Operative Day 14 (POD 14)**

- Side Effects

**7.0 STATISTICAL ANALYSIS**

- Proposed analysis: T-Test
- Interim analysis planned: Yes, at the 50% mark of 56 patients
- Alpha level: 0.05
- Beta or power level: 0.8
- Primary outcome variable estimate (mean +/- s.d. for continuous outcome, frequency/percentage for categorical variable): Mean difference of 1.3 +/- 1.0
- Number of groups being compared: 2
- Effect size or change expected between groups: Noninferior margin of 1.3
- Resulting number per group: 51
- Total sample size required: 102 + 10% (for attrition/withdrawal) = 112

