## PROTOCOL SYNOPSIS

Protocol Title:	Prolonging the Interscalene brachial plexus block by adding liposomal bupivacaine or preservative free dexamethasone to bupivacaine: a non-inferiority trial
Protocol Number:	2019_0424
Protocol Date:	5/28/2021
Sponsor:	Department of Anesthesiology
Principal Investigator:	[name]
Objective:	The intervention being studied is the usage of liposomal bupivacaine in conjunction of standard bupivacaine in an interscalene block (ISB). It is being compared to standard bupivacaine. Does the mixture of liposomal bupivacaine and bupivacaine provide extended analgesia in comparison to bupivacaine with preservative free dexamethasone?
Study Design:	Randomized Controlled Clinical Trial
Enrollment:	112
Subject Criteria:	
 
1. Patients scheduled for elective outpatient arthroscopic shoulder surgery
 
2. ASA I-III
 
3. Ages 18 years or older
 

Data Collection:	
Sources: EPIC, Medical Records, and Patient Reported.
 
Variables: Demographics, Surgery type, Incidence of adverse effects (Horner's, hoarseness, dyspnea, hiccups), sensory exam (alcohol swab), motor exam (handgrip strength: present/weak/absent), NRS Pain scores at rest and at movement, Patient satisfaction, Opioid Consumption, Neuropraxia, Nerve Block Success, Length of PACU stay, Time to meet discharge criteria, Post Anesthetic discharge scoring system (assessed every 15 min after one hour in PACU, Brief Pain Inventory short form, LAST (local anesthetic systemic toxicity), Admission for pain.

Statistical Analysis:	
 
• Alpha level: 0.05
 
• Beta or power level: 0.8
 

---

	

• Primary outcome variable estimate (mean +/- s.d. for continuous outcome, frequency/percentage for categorical variable): Mean difference of 1.3 +/- 1.0

• Interim analysis at 50% enrollment mark

• Proposed analysis: T-Test

• Effect size or change expected between groups: Noninferior margin of 1.3

• Total sample size required: 102 + 10% (for attrition/withdrawal) = 112

--	---

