### 3.0 STUDY HYPOTHESES

The prolongation of analgesia provided by adding liposomal bupivacaine to bupivacaine is non-inferior to Bupivacaine with preservative free dexamethasone.

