### 4.0 STUDY DESIGN

#### 4.1 Endpoints

##### 4.1.1 Primary Endpoint

- The primary outcome is average NRS pain score at rest over 72 hours (average of 3 24-hour time point [24, 48, 72 hours]).

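### The primary comparison is an unadjusted t-test although preoperative NRS is already collected; adjusting for it would probably narrow the interval set against the 1.3 margin, at almost no cost

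*Combined protocol and SAP*

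**What the plan says.** Section 4.1.1 defines the endpoint: "The primary outcome is average NRS pain score at rest over 72 hours (average of 3 24-hour time point [24, 48, 72 hours"]). Section 3.0 states the hypothesis as non-inferiority: "The prolongation of analgesia provided by adding liposomal bupivacaine to bupivacaine is non-inferior to Bupivacaine with preservative free dexamethasone". Section 7.0, repeated in most respects by the synopsis, gives the analysis in a short list:

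- "Proposed analysis: T-Test"
- "Alpha level: 0.05", with power 0.8
- "Mean difference of 1.3 +/- 1.0"
- "Effect size or change expected between groups: Noninferior margin of 1.3"
- "Resulting number per group: 51"
- one interim analysis, at 56 patients

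No covariate is named. The pre-operative list in section 6.3 includes a preoperative NRS, without saying whether it is taken at rest or with movement. The synopsis lists "NRS Pain scores at rest and at movement" among the variables but does not tie either form to the preoperative assessment. The secondary endpoints attach the two forms only to the PACU and later days.

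**The concern.** The result of a non-inferiority trial turns on one confidence limit, here the upper limit for liposomal minus dexamethasone set against 1.3. Anything that legitimately shortens the interval makes that decision more reliable. A baseline measure of the outcome is the usual candidate, and this trial already records one without giving it a use in the analysis. What is at stake is precision, and through it power, if the true SD is larger than 1.0 or the true difference lies closer to the margin than 0. The validity of the conclusion is not at stake.

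**Working it through.** **Inputs.** From section 7.0: margin 1.3, SD 1.0, 51 per group, alpha 0.05 (sidedness not stated), power 0.8. Assumed here because the documents do not give them: true difference 0; correlation r between preoperative NRS and the 72-hour mean of 0, 0.2, 0.3 or 0.5; and an alternative SD of 2.6.

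**Step 1: the plan's own figure.** With margin 1.3, SD 1.0, true difference 0 and the noncentral t, 80% power needs 9 per group at one-sided 0.05 (8 gives 79.6%, 9 gives 84.0%) or 11 at one-sided 0.025 (10 gives 78.5%, 11 gives 82.6%). The printed 51 is not reproduced. At 51 per group, 80% power corresponds to an SD of about 2.62 at one-sided 0.05 or about 2.32 at one-sided 0.025. This is why SD 2.6 is tried beside the printed 1.0.

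**Step 2: formulas.**

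- Unadjusted: SE = SD × √(2/51) = SD × 0.1980, with 100 df.
- Adjusted: SE = SD × √(1 − r²) × 0.1980 × √(1 + 1/98), with 99 df. The last factor, 1.0051, is the price of estimating the slope.
- Half-width = t quantile × SE. For a two-sided 95% interval the quantile is 1.984 at both 100 and 99 df.
- Power = P(T > t quantile), where T is noncentral t with noncentrality 1.3/SE.

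**Step 3: results with 51 per group.**

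| Analysis | 95% half-width, SD 1.0 | SE, SD 2.6 | Noncentrality | Power, one-sided 0.05 | Power, one-sided 0.025 |
|---|---|---|---|---|---|
| Unadjusted | 0.393 | 0.515 | 2.525 | 80.6% | 70.6% |
| ANCOVA, r = 0 | 0.395 | 0.517 | 2.512 | 80.2% | 70.1% |
| ANCOVA, r = 0.2 | 0.387 | 0.507 | 2.564 | 81.6% | 71.9% |
| ANCOVA, r = 0.3 | 0.377 | 0.494 | 2.633 | 83.4% | 74.1% |
| ANCOVA, r = 0.5 | 0.342 | 0.448 | 2.901 | 89.2% | 81.9% |

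At SD 1.0 and a true difference of 0, power exceeds 99.9% in every row at either level. The powers shown for SD 2.6 also apply at SD 1.0 if the true difference is 0.8, because (1.3 − 0.8)/1.0 = 1.3/2.6 = 0.5.

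**Step 4: break-even.** Ignoring the negligible change in the t quantile, adjustment helps when (1 − r²)(1 + 1/98) < 1, that is r² > 1/99, or r above about 0.10.

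**The case against.** The strongest reply is that the t-test is valid and that, on the printed figures, adjustment hardly matters. At SD 1.0 and r = 0.3 the half-width shrinks by 0.393 − 0.377 = 0.016 NRS points against a margin of 1.3, and power is near 100% either way. The larger gains need an SD of 2.6 or a true difference of 0.8, together with a correlation; none of these is in the documents. Below r of about 0.10, adjustment loses a little. All of this stands, and it limits the point to a low-cost improvement. It does not remove the point, because the printed inputs do not lead to 51 per group and so are not a secure basis for dismissing precision.

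A second reply is that the preoperative score may not be taken at rest. That also stands: section 6.3 does not say, and the synopsis list does not settle it. The covariate has to be worded to allow for either case.

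A reader might also infer that one-sided 0.05 was intended, because a standardized effect of 0.5 at that level gives exactly 51 per group (at one-sided 0.025 it needs 64). The documents do not support this. Neither that effect nor an SD of 2.6 is printed, and an SD of about 2.32 at one-sided 0.025 fits 51 equally well. The opposite inference, that one-sided 0.025 is a safe default because power stays near 100%, relies on SD 1.0; at SD 2.6 the unadjusted power is 70.6%.

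**Conclusion.** The point holds as a recommendation about precision. An already collected baseline score is left out of the primary analysis, and including it would probably narrow the interval compared with 1.3. At the printed SD and a true difference of 0 the benefit is a slightly shorter interval and no practical change in power. At an assumed SD of 2.6, it is 1.0, 2.8 or 8.6 points of power at one-sided 0.05 for assumed correlations of 0.2, 0.3 or 0.5, against a loss of about 0.4 points if the correlation is zero.

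Two stronger readings are not supported. The first is that the t-test is wrong or that the trial will test superiority: the title, the hypothesis in section 3.0 and the stated margin make a comparison with 1.3 the natural reading, and an unadjusted comparison of randomized groups is valid. The second is that adjustment is certain to help, which the documents cannot show without a correlation.

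A secondary clarification is needed. The plan does not say whether alpha 0.05 is one-sided or two-sided, or what part the interim analysis at 56 patients plays in that level. The level cannot be recovered from 51 per group, so only the sponsor can state it.

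**What to change.** In section 7.0 and the synopsis, replace the t-test for the primary endpoint with wording such as:

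> ANCOVA of the mean of the 24, 48 and 72 h NRS at rest on treatment and preoperative NRS (the at-rest score if it is recorded, otherwise the preoperative NRS as collected). A missing preoperative NRS is replaced by the mean over all randomized patients. Non-inferiority is judged by comparing the upper confidence limit for liposomal minus dexamethasone with 1.3. The unadjusted difference is reported as a sensitivity analysis.

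State in section 6.3 which form of preoperative NRS is recorded. In the same edit, the sponsor should state the sidedness of alpha 0.05 and the role of the interim analysis in that level; no default is proposed here. All of this should be fixed before outcomes are seen by group.

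The cost is a few sentences, with no added visits or patients and no new data item, since the score is used as collected. The statistical price is one degree of freedom and the small loss at zero correlation shown above. The missing-baseline rule costs little: with 10% missing at random (assumed), SD 2.6, r = 0.5 and one-sided 0.05, simulation of 40,000 trials gave power of 88.1% instead of 89.2%, with an error rate of 4.9% at a true difference of 1.3.

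### The stated planning inputs (margin 1.3, SD 1.0, alpha 0.05, power 0.8, t-test) give 9 or 11 patients per group at a true difference of 0, not 51

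*Combined protocol and SAP*

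**What the plan says.** Section 7.0 Statistical Analysis contains the whole sample-size justification as a list:

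- Test: "Proposed analysis: T-Test", two groups.
- Error rates: "Alpha level: 0.05", with no statement of one- or two-sided, and "Beta or power level: 0.8".
- Outcome estimate: "Primary outcome variable estimate (mean +/- s.d. for continuous outcome, frequency/percentage for categorical variable): Mean difference of 1.3 +/- 1.0".
- Effect: "Effect size or change expected between groups: Noninferior margin of 1.3".
- Result: "Resulting number per group: 51".

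The synopsis repeats these figures apart from the per-group number, including "Mean difference of 1.3 +/- 1.0" and "Total sample size required: 102 + 10% (for attrition/withdrawal) = 112". Neither place gives a formula, software, a source for the SD, or an assumed true difference distinct from the margin. Sections 3.0 and 4.1.1, which state the hypothesis and the primary endpoint, add no planning value.

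**The concern.** A margin of 1.3 with an SD of 1.0 is a standardised distance of 1.3, which is very large. A t-test detects a distance of that size with roughly ten patients per group, so 51 stands out at once.

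The value 1.3 is also entered twice, once as the estimated mean difference and once as the margin. The reader cannot tell whether a non-zero true difference was assumed.

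This list is the only quantitative reason given for enrolling 112 patients. If its inputs do not lead to its result, the 80% power cannot be verified. Depending on which input is corrected, 51 per group may be about five times what is needed, about right, or too few for 80% power.

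**Working it through.** **Inputs.** All are from Section 7.0 unless marked.

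- Margin M = 1.3
- SD = 1.0, read from the field labelled mean and s.d.
- Power 0.80, two equal groups, two-sample t-test
- Alpha 0.05, sidedness not stated; both one-sided 0.05 and one-sided 0.025 (two-sided 0.05) are tried
- True difference D (liposomal minus dexamethasone) = 0: an assumption, as the plan states none

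**Formula.** Power = P(T > t_crit), where t_crit is the one-sided critical value of t with 2n − 2 degrees of freedom, and T is noncentral t with the same degrees of freedom and noncentrality (M − D) / (SD × √(2/n)).

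**Step 1: try to reproduce 51.** With M − D = 1.3 and SD = 1.0:

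| One-sided alpha | n per group | Noncentrality | Power |
|---|---|---|---|
| 0.05 | 8 | 1.3/√(2/8) = 2.60 | 79.6% |
| 0.05 | 9 | 1.3/√(2/9) = 2.76 | 84.0% |
| 0.025 | 10 | 1.3/√(2/10) = 2.91 | 78.5% |
| 0.025 | 11 | 1.3/√(2/11) = 3.05 | 82.6% |
| 0.05 | 51 | 1.3/√(2/51) = 6.56 | 99.9999% |
| 0.025 | 51 | 6.56 | 99.9997% |

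The required n is 9 or 11. The ratio 51/11 is 4.6 and 51/9 is 5.7, so rounding cannot explain the gap.

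**Step 2: try other readings of the stated numbers.** n per group at one-sided 0.05 / 0.025:

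- 1.3 read as a difference to be detected in a superiority test, at the same one-sided level: same noncentrality, 9 / 11
- 90% power: 11 / 14
- Alpha halved for the interim look: 11 / 13
- SD taken as √2: 16 / 20
- 1.3 and 1.0 exchanged (margin 1.0, SD 1.3): 22 / 28
- 1.3 taken as the true unfavourable difference: M − D = 0, so no finite n reaches 80%

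None gives 51.

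**Step 3: find what would give 51.** Values for which the smallest n reaching 80% is 51:

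- D = 0: SD about 2.60 to 2.62 (one-sided 0.05) or 2.30 to 2.32 (one-sided 0.025)
- SD = 1.0: D about 0.80 (one-sided 0.05) or just under 0.74 (one-sided 0.025), against liposomal bupivacaine

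None of these values is stated in the plan.

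**Step 4: how much the missing input matters.** D = 0; every SD other than 1.0 is an assumption. Each cell gives one-sided 0.05 / one-sided 0.025.

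| SD | Power at 51 per group | n per group for 80% |
|---|---|---|
| 1.0 | >99.99% / >99.99% | 9 / 11 |
| 2.0 | 94.7% / 90.2% | 30 / 39 |
| 2.3 | 88.3% / 80.7% | 40 / 51 |
| 2.6 | 80.6% / 70.6% | 51 / 64 |
| 3.0 | 70.1% / 58.2% | 67 / 85 |

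At SD 2.6 the unstated sidedness alone moves power by 80.6 − 70.6 = 10 percentage points. All these figures assume that no alpha is spent at the interim look.

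**The case against.** The strongest reply is that the 9 and 11 rest on two readings. The plan does not state a true difference of 0, and a spread attached to a mean difference need not be the between-patient SD of the outcome. Moreover, 51 is exactly what a one-sided 0.05 t-test with 80% power needs for a standardised distance of 0.5 (power 80.6%), and both one-sided 0.05 solutions reduce to that case: 1.3/2.6 = 0.5 and (1.3 − 0.8)/1.0 = 0.5. That suggests a coherent calculation that was badly transcribed.

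This is fair as a guess about how 51 arose, but it does not restore the stated basis. A distance of 0.5 still needs an SD or a true difference that the plan omits. The only difference the plan does state is 1.3, which equals the margin. If 1.0 is not the outcome SD, then it is mislabelled, because the field calls it an s.d.

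A second reply is that the test remains valid and that, read literally, the plan is over-powered rather than under-powered. Both statements are true. Power below 80% at D = 0 appears only with assumed SDs, above about 2.6 at one-sided 0.05 or about 2.3 at one-sided 0.025. The finding is therefore not that 51 is too few or too many, but that the stated inputs do not deliver the stated n and power.

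A third reply is that keeping 51 before the SD is known puts the answer ahead of the question. What stands of this is that, once the inputs are written down, a power below 80% must be either accepted openly or met with a larger sample.

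**Conclusion.** The concern holds, and the sample-size statement must be corrected. The plan's margin, SD, alpha, power and test give 9 (one-sided 0.05) or 11 (one-sided 0.025) per group, against 51 stated. At 51 per group they give power above 99.99%, against 80% stated. This rests on a true difference of 0 and on reading 1.0 as the outcome SD.

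Relaxing either assumption can recover 51, but only with a value the plan does not contain. The documents do not allow the faulty input to be identified. The type I error of the final non-inferiority test is not affected by this point.

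**What to change.** In the synopsis and in Section 7.0, replace "Mean difference of 1.3 +/- 1.0" with the inputs actually used, for example:

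> SD [value, with source]; assumed true difference, liposomal minus dexamethasone, [value]; non-inferiority margin 1.3; one-sided alpha [0.05 or 0.025]; 51 per group; power [value].

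Remove 1.3 as the expected difference unless a true difference of that size is really meant. Keep 51 per group and report the power that these inputs deliver. At a true difference of 0 that is:

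- SD 1.0: above 99.99%
- SD 2.3: 88% (one-sided 0.05) or 81% (one-sided 0.025)
- SD 2.6: 81% (one-sided 0.05) or 71% (one-sided 0.025)

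If the interim look spends alpha, the power should be computed with that included.

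The cost is wording in two places. The restated power may be less favourable than 80%. At SD 2.6 and one-sided 0.025, for instance, holding 80% would need 64 per group instead of 51, or 2 × 64 = 128 instead of 102 before attrition.

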**8.0 ADVERSE EVENT ASSESSMENT**

All Adverse Events (AEs) will be reported in the final study report.
